Appendix E. Study Activities (Substudy 3)

Activity	Baseline of Substudy 3 ^a	Week 4	Week 8	Week 12	Week 20	Week 28	Week 36	Week 44	Week 52/ Premature Discontinuation Visit	Unscheduled Visit ^b	30-Day Follow-Up ^c
Informed Consent	X ^d										
Prior and Concomitant Medications [#]	X	X	X	X	X	X	X	X	X	X	
Physical Exam ^{e,+}	X	X	X	X	X	X	X	X	X	X	
Vital Signs ^{f,#}	X ^f	X	X	X	X	X	X	X	X ^f	X	
Schedule Endoscopy [#]								X			
Endoscopy/Biopsy ^{g,+}	X								X		
12-Lead ECG ⁺	X								X		
Chest X-Ray ^{h,+}									X		
Chemistry and Hematology ^{i,+}	X	X	X	X	X	X	X	X	X	X	
Lipid Test ^{t,+}	X				X				X		
Urinalysis ^{l,+}	X	X	X	X	X	X	X	X	X	X	
Pregnancy Test ^{k,+}	X	X	X	X	X	X	X	X	X	X	X

Activity	Baseline of Substudy 3 ^a	Week 4	Week 8	Week 12	Week 20	Week 28	Week 36	Week 44	Week 52/ Premature Discontinuation Visit	Unscheduled Visit ^b	30-Day Follow-Up ^c
Review and document continued compliance with pregnancy avoidance recommendations in the source records with females of childbearing potential [#]	X	X	X	X	X	X	X	X	X	X	X
hs-CRP ⁼	X	X	X	X	X	X	X	X	X	X	
Latent TB Risk Assessment Form [#]				X					X		
PPD Skin Test or QuantiFERON-TB Gold Plus Test ⁺									X ⁿ		
Provide Stool Kit ^{n,#}	X	X		X				X			
Stool Sample (Fecal calprotectin) ^{n,=}	X	X	X		X				X		
Upadacitinib Concentration (PK assay) ^{o,=}	X						X		X		
HBV DNA PCR (For Japan subjects only) ^{p,+}		X		X	X	X	X	X	X		

Activity	Baseline of Substudy 3 ^a	Week 4	Week 8	Week 12	Week 20	Week 28	Week 36	Week 44	Week 52/ Premature Discontinuation Visit	Unscheduled Visit ^b	30-Day Follow-Up ^c
Reminder: Samples for exploratory research and validation studies (Optional – see Appendix F) [†]		X		X		X		X	X		
Mayo Score [#]	X								X		
Partial Mayo Score [#]	X	X	X	X	X	X	X	X	X	X	
Patient Questionnaires: IBDQ, SF-36, EQ-5D-5L, WPAI, PGIC, FACIT-F, UC-SQ, PGIS ^{q,†}	X								X		
Monitor Adverse Events ^{r,†}	X	X	X	X	X	X	X	X	X	X	X
Daily Diary Review ^{s,†}	X	X	X	X	X	X	X	X	X	X	
Study Drug Dispensing/Administration ^{t,u,†}	X	X	X	X	X	X	X	X			

EQ-5D-5L = European Quality of Life 5 Dimensions 5 Levels; FACIT F = Functional Assessment of Chronic Illness Therapy – Fatigue; IBDQ = Inflammatory Bowel Disease Questionnaire; PGIC = Patient Global Impression of Change; PGIS = Patient Global Impression of Severity; SF-36 = Short-Form 36; UC-SQ = Ulcerative Colitis Symptoms Questionnaire; WPAI = Work Productivity and Activity Impairment

- # Study activity that can be performed by phone/virtually when an onsite study visit is not possible due to COVID-19, if allowed by local regulations. This is applicable for all Substudy 3 visits.
- + Study activity that can be performed at a local centre when an onsite study visit is not possible due to COVID-19, if allowed by local regulations. This is applicable for all Substudy 3 visits.
- = Study activity that cannot be performed by phone/virtually or at a local centre when an onsite study visit is not possible due to COVID-19. This is applicable for all Substudy 3 visits.

- a. Subjects in Substudy 1, Substudy 2 Part 1, or Study M14-675 Part 1 who achieved response after completion of the 8-week induction treatment will be enrolled into Substudy 3. The Baseline Visit for Substudy 3 corresponds to the Week 8 Visit in Substudy 1 or Substudy 2 and serves as the reference for all subsequent visits. Subjects in Substudy 2 Part 2 or Study M14-675 Part 2 who achieved response after completion of the Extended Treatment Period (Week 16) will be enrolled into Substudy 3 and the Baseline Visit for Substudy 3 corresponds to the Week 16 Visit and serves as the reference for all subsequent visits except for PK. The PK sample collected at Week 8 of induction will be the baseline for Substudy 3. A \pm 3-day window is permitted around scheduled study visits up to and included Week 12. Following completion of the Week 12 visit, a \pm 7-day window is permitted around scheduled study visits. Where COVID-19 affects an onsite scheduled Visit a \pm 7-day window is permitted for all visits after the Baseline visit.
- b. Visits for dispensing new study drug in case of temperature excursion, loss or damage are not considered an Unscheduled Visit.
- c. Subjects who do not continue into the Study M14-533 will be contacted 30 days following study drug discontinuation for an assessment of any new or ongoing AEs. The home pregnancy test results will be reported at this visit and if a pregnancy is identified, the pregnancy must be reported to AbbVie as outlined in Section 6.1.6. The 30 day follow up visit should not take place sooner than 30 days after the last dose of study drug, the allowable visit window is only for 30 days or later and is dependent upon what phase of the study the subject was at when discontinuing study drug. A + 3 day window is allowed up to Week 12 (30 - 33 days after last dose of study drug) and a + 7 day window is allowed after Week 12 (30 to 37 days after last dose of study drug).
- d. For US subjects only: subjects will be enrolled into Substudy 3 only after written informed consent is obtained. For subjects entering Study M14-234, Substudy 3 from Study M14-675, a new consent will be required.
- e. Physical examinations performed at Baseline, Week 52 and PD Visits are full physical examinations which must include an assessment of extra-intestinal manifestations (EIMs). Physical exams at all other visits are symptom-based as necessary. Assessment of EIMs are required at every visit.
- f. For Subjects 16 or 17 years of age at the time of screening, height (with shoes off) will be measured at Substudy 3 Week 0 and Week 52.
- g. Subjects will undergo an endoscopy (colonoscopy or flexible sigmoidoscopy, depending on the extent of disease at Screening in Substudy 1 or 2) with biopsy for histologic assessment at Baseline and at Week 52/PD. The local endoscopy reading will be utilized to determine the status of clinical remission for the purpose of treatment assignment in Study M14-533. During all endoscopies, up to 3 sets of biopsies will be taken (see Section 5.3.1.1 for details about biopsy sampling). For subjects who discontinue during the maintenance period (Substudy 3), an endoscopy will not be performed if the subject discontinues the study prior to the Week 28 Visit. Where COVID-19 affects the Week 52 endoscopy a -2 week and +4 week window is permitted.
- h. A CXR will be performed at Week 52/PD for subjects with a positive response to TB risk questionnaire, Part 1 questions or for subjects with newly positive PPD and/or QuantiFERON-TB Gold Plus test after baseline.
- i. It is requested to have a minimum of 8 hours fasting before chemistry or lipid test.
- j. The Central Laboratory will perform the urinalysis macro and micro (if applicable). A microscopic analysis will be performed by the central laboratory, in the event the dipstick results show leukocytes, nitrite, ketone, protein, blood or glucose value of greater than a trace. Sites will not be provided with urinalysis dipsticks.

- k. Urine pregnancy test will be performed at Baseline and all subsequent visits for all women of child bearing potential. In home urine pregnancy test will be completed at Weeks 16, 24, 32, 40, 48 and the 30-Day Follow-up Visit. The results of the monthly at home tests will be communicated to the site. If any urine pregnancy test is positive, a serum pregnancy test will be performed by the central laboratory. If a pregnancy is identified, the pregnancy must be reported to AbbVie as outlined in Section 6.1.6.
- l. QuantIFERON-TB Gold Plus test is to be carried out annually from the date of the original test carried out at screening. For subjects with premature discontinuation if the Premature Discontinuation visit is ≤ 12 weeks from the prior TB test and no new known exposure of risk identified then the TB test does not need to be repeated. If the Premature Discontinuation visit is > 12 weeks from the prior TB test, the TB test will be repeated at the Premature Discontinuation visit.
- m. If an annual TB test is newly positive (seroconversion), a chest x-ray (CXR) needs to be performed as soon as possible to aid in distinguishing active versus latent TB, and subsequent annual TB follow-up tests are not required.
- n. Stool sample will be collected at each time point indicated. For the visit where endoscopy will be conducted, stool sample should be collected prior to endoscopy. If a sample cannot be obtained during the site visit, the site will give instructions and a stool sample supply kit (supplies will be provided at the time-points indicated). All stool samples should be collected before any bowel preparation for endoscopy is started and should be returned to the site within 3 days of collection.
- o. PK samples should be collected at any time during the visit. Subject should follow the regular dosing schedule. The PK sample drawn at Week 8 of Induction will be the baseline PK sample for Substudy 3.
- p. For Japan subjects only: Subjects with positive HBs Ab and/or positive HBc Ab results at Screening in Substudy 1 or 2 should have HBV-DNA PCR test performed at Weeks 4, 12, 20, 28, 36, 44, and 52/PD in Substudy 3; in cases where recurrence of HBV-DNA is observed, the subject should be discontinued from the study. This measure is not necessary in patients with history of HBV vaccination and positive HBs Ab result. HBV testing is done every 12 weeks where required.
- q. IBDQ, SF-36, EQ-5D-5L, WPAI, FACIT F, PGIC, UC-SQ will only be collected from subjects at select sites for subjects entering from Substudy 1, for subjects entering from Substudy 2 or Study M14-675, this will be completed at all sites; PGIS = Patient Global Impression of Severity will only be collected from subjects at select sites.
- r. During each study visit subjects will also be asked to report UC related Health Care Resource Utilization (Unscheduled Outpatient Visits, Emergency Room Visits and Hospitalizations and surgeries) and will be captured as a part of supplemental HCRU form of AE collection in EDC.
- s. Subjects will continue to use the diary dispensed to them at Screening of Study M14-234 Substudy 1 or Substudy 2 or Study M14-675. All subjects should complete their subject diary on a daily basis throughout the entire study, including during hospitalizations whenever possible. The diary will be reviewed by site personnel with the subject at each visit and collected at the Final/PD Visit.
- t. Study drug will be dispensed for once daily oral intake and should be taken at the same time each day, when possible.
- u. When central or local labs cannot be collected as scheduled in the protocol during the period of COVID-19 pandemic, drug may be dispensed if the following criteria are confirmed. (1) There is at least 1 post-Week 0 lab test AND (2) The investigator feels it is safe to continue based on prior labs and a phone/video call AND (3) No longer than 12 weeks have passed from the last safety lab tests.

Appendix F. Study Activities (Substudy 3) Optional Samples for Exploratory Research and Validation Studies

Activity	Baseline of Substudy 3	Week 4	Week 8	Week 12	Week 20	Week 28	Week 36	Week 44	Week 52/ Premature Discontinuation Visit	Unscheduled Visit	30-Day Follow-Up
Epigenetic samples ^a		X		X		X		X	X		
Transcriptomic and epigenetic samples ^{a,b}		X		X		X		X	X		
Plasma samples for proteomic and targeted protein investigations ^{a,b}		X		X		X		X	X		
Serum samples for proteomic and targeted protein investigations ^{a,b}		X		X		X		X	X		
Tissue biopsy samples for transcriptomic, epigenetic, and exploratory research									X		

a. Based on the value of the different technologies, samples may also be used to assess other biomarker signatures, including but not limited to metabolomics, lipidomics, and other approaches.

b. Preferably collected while subjects are in a fasting condition.

Note: Collections to be performed only if subject provides written consent to collect the exploratory research/validation studies samples; if the consent is not signed, no samples can be collected.

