* A positive test result for HBs Ab is expected for subjects who have had a HBV vaccination. For subjects without a history of HBV vaccination (and for subjects in Japan) a positive result for HBs Ab/anti-HBs requires HBV DNA PCR testing.

** Where mandated by local requirements; subjects with HBs Ab+ and/or HBc Ab+ and negative HBV DNA at Screening should have HBV DNA PCR testing performed approximately every 12 weeks. HBV DNA PCR testing every 12 weeks is not necessary when the subject has a history of HBV vaccine and HBs Ab+ and HBc Ab-. If necessary, HBV DNA PCR may be tested at unscheduled visits.

COVID-19 Pandemic-Related Acceptable Protocol Modifications

In the event that the HBV DNA PCR cannot be performed for subjects who require the test due to study modifications related to the COVID-19 pandemic, perform the HBV

DNA PCR at the next earliest feasible visit or arrange to have it completed by a local laboratory.

Hepatitis C

Blood samples for hepatitis C serology will be obtained at the Screening Visit. A positive HCV Ab will trigger an HCV RNA test. A subject will not be eligible for study participation if test results indicate active hepatitis C (HCV RNA detectable in any subject with anti HCV Ab).

HIV

Subjects with HIV infection (positive HIV test) are excluded from study participation. An anti-HIV antibody (Ab) test will be performed at Screening, unless prohibited by local regulations. The investigator must discuss any local reporting requirements to local health agencies with the subject. The site will report confirmed positive results to their health agency per local regulations, if necessary. If a subject has a confirmed positive result, the investigator must discuss with the subject the potential implications to the subject's health and subject should receive or be referred for clinical care promptly. **AbbVie will not receive results from the testing and will not be made aware of any positive result.**

Clinical Laboratory Tests

Blood samples will be obtained for the laboratory tests listed in [Table 1](#). Tests should always be performed only after all clinical assessments, questionnaires (Inflammatory Bowel Disease Questionnaire [IBDQ], etc.) and vital sign determinations are obtained during a visit.

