AST or ALT	
 • Interrupt study drug immediately if confirmed ALT or AST $> 3 \times$ ULN by repeat testing with new sample and either a total bilirubin $> 2 \times$ ULN or an international normalized ratio (INR) > 1.5. 
 ○ A separate blood sample for INR testing will be needed to measure INR at the time of repeat testing for ALT or AST. A repeat test of INR is not needed for determination if above toxicity management criteria are met. • Interrupt study drug immediately if confirmed ALT or AST $> 3 \times$ ULN by repeat testing with new sample along with appearance of fatigue, nausea, vomiting, right upper quadrant pain or tenderness, fever, rash, and/or eosinophilia ($> 5\%$). • Interrupt study drug immediately if confirmed ALT or AST $> 5 \times$ ULN by repeat testing with new sample for more than 2 weeks. • Interrupt study drug immediately if confirmed ALT or AST $> 8 \times$ ULN by repeat testing with new sample. • Subjects with HBc Ab+ (irrespective of HBs Ab status) and negative HBV DNA PCR testing at screening who develop the following should have HBV DNA by PCR testing performed within 1 week (based on initial elevated value): 
 ○ ALT $> 5 \times$ ULN OR ○ ALT or AST $> 3 \times$ ULN if an alternative cause is not readily identified. 
 • A separate blood sample for HBV DNA PCR testing will be needed at the time of repeat testing for ALT or AST. 
A positive result for HBV DNA PCR testing in these subjects will require immediate interruption of study drug (unless not acceptable by local practices) and a hepatologist consultation should occur within one week for recommendation regarding subsequent treatment.
 
Subjects who meet any of the above criteria should be evaluated for an alternative etiology of the ALT or AST elevation and managed as medically appropriate. If applicable, the alternative etiology should be documented in the eCRF. If ALT or AST values return to the normal reference range or its Baseline value, study drug may be restarted. If restarting study drug, documentation should include reason that rechallenge is expected to be safe. If after clinically appropriate evaluation, no alternative etiology for ALT or AST elevation is found or the ALT or AST elevation has not resolved or is not trending down toward normal, the subject should be discontinued from study drug.
 
For any confirmed ALT or AST elevations > 3 ULN, complete supplemental hepatic eCRF

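### For Japan subjects, the exemption from scheduled on-treatment HBV-DNA testing is stated in two incompatible ways: one requires a negative HBc Ab, the other does not mention HBc Ab

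*Protocol*

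**What the plan says.** All of the text is in the Protocol.

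- **Enrolment (Section 5.3.1.1, Hepatitis B).** A positive HBc Ab triggers a reflex HBV-DNA PCR. If HBV DNA is negative, the subject may be enrolled.
- **Figure 4, double-asterisk note (Section 5.3.1.1).** "Where mandated by local requirements; subjects with HBs Ab+ and/or HBc Ab+ and negative HBV DNA at Screening should have HBV DNA PCR testing performed" about every 12 weeks. The exemption reads "HBV DNA PCR testing every 12 weeks is not necessary when the subject has a history of HBV vaccine and HBs Ab+ and HBc Ab". That quotation stops just before the minus sign after HBc Ab, so the third condition is a negative HBc Ab.
- **Appendix E footnote p (Japan only, Substudy 3).** The scope reads "Subjects with positive HBs Ab and/or positive HBc Ab results at Screening in Substudy 1 or 2 should have HBV-DNA PCR test performed at Weeks", and the list of weeks given there is 4, 12, 20, 28, 36, 44 and 52/PD. If HBV DNA recurs, the subject is to be removed from the study. The exemption is "This measure is not necessary in patients with history of HBV vaccination and positive HBs Ab result". The footnote closes with "HBV testing is done every 12 weeks where required".
- **Appendix C footnote s (Japan only, induction Week 8).** It repeats the exemption and the removal rule of footnote p.
- **Section 6.1.7, Table 5 (AST or ALT).** HBc Ab-positive subjects, whatever their HBs Ab status, who were HBV-DNA negative at screening and develop defined ALT/AST elevations get an HBV-DNA test within a week. "A positive result for HBV DNA PCR testing in these subjects will require immediate interruption of study drug (unless not acceptable by local practices"), with a hepatologist consulted within a week.

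**The concern.** Elsewhere the Protocol treats HBc Ab as a marker in its own right: it triggers the screening PCR, and it defines the Table 5 population irrespective of HBs Ab. An exemption from scheduled testing that does not mention HBc Ab does not fit that approach, and it departs from the exemption in the Figure 4 note.

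At stake is whether a site can tell from the Protocol if an HBc Ab-positive, HBV-DNA-negative subject is due scheduled HBV-DNA tests through up to 52 weeks of maintenance treatment. Enrolment into Substudy 3 is closed (Section 4.0). However, Section 8.1 keeps any subject unfinished at database lock on blinded treatment until completion, so the instruction can still matter.

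**Working it through.** No power or alpha calculation applies. The check applies each rule, as written, to every serology and vaccination pattern.

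**Inputs.** V = history of HBV vaccination, S = HBs Ab positive, C = HBc Ab positive. HBV DNA is negative at screening (needed for enrolment when C is yes).

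- Figure 4 note, where mandated: test if (S or C), unless (V and S and not C).
- Appendix E footnote p and Appendix C footnote s, Japan: test if (S or C), unless (V and S).

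| V | S | C | Figure 4 note | Appendices C and E |
|---|---|---|---|---|
| no | no | no | no test | no test |
| no | no | yes | test | test |
| no | yes | no | test | test |
| no | yes | yes | test | test |
| yes | no | no | no test | no test |
| yes | no | yes | test | test |
| yes | yes | no | no test | no test |
| yes | yes | yes | **test** | **no test** |

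The rules agree in 7 of 8 patterns and differ in exactly one.

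**Number of scheduled tests for that pattern in Substudy 3.**

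- Footnote p visit list, if the exemption did not apply: Weeks 4, 12, 20, 28, 36, 44, 52 = 7 tests. Each gap is 8 weeks (12 − 4, 20 − 12, and so on to 52 − 44).
- Figure 4 note, about every 12 weeks: 52/12 = 4.3, so 4 tests (Weeks 12, 24, 36, 48), or 5 if Week 52/PD is added.
- Footnote p with its exemption as written: 0.

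In induction, Appendix C footnote s gives 1 test (Week 8) without the exemption and 0 with it.

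**Secondary drafting points, passages side by side.**

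- *Source study.* Footnote p refers to results "at Screening in Substudy 1 or 2 should have HBV-DNA PCR test performed at Weeks 4, 12, 20, 28, 36, 44, and 52/PD". Substudy 3 also takes responders from Study M14-675 (Section 5.1.2). Footnotes a, d, q and s of Appendix E name M14-675; footnote p does not. The table row to which footnote p is attached is limited to Japan but not by study of origin.
- *Interval.* The 8-weekly list and the 12-week sentence stand in one footnote, and nothing says to whom the 12-week sentence applies.
- *Action on a positive result.* A Japan HBc Ab-positive subject within footnote p, with an ALT/AST elevation that meets Table 5 and a positive PCR, falls under both rules: removal from the study (footnote p) and interruption of study drug with a hepatology consultation (Table 5). No precedence is stated.

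**The case against.** The strongest defence of the text is that the appendix exemption is shorthand. Section 5.3.1.1 labels the vaccinated, HBs Ab-positive subject Scenario B and places Scenario B among the HBc Ab-negative cases; HBc Ab-positive cases are Scenarios C and D. On that reading, all three places exempt the same people. This is plausible, but neither appendix footnote refers to the scenarios or mentions a negative HBc Ab, and a site working from the schedule sees only the footnote. The Figure 4 diagram was not available in the text reviewed, so its boxes could not be checked.

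Several stronger readings are tempting, and the documents do not support them:

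- *That the Figure 4 note makes the test compulsory for this subject.* It is worded as a recommendation and applies only where local requirements mandate testing. The Protocol does not say whether Japan has such a requirement.
- *That the exempted subject is unmonitored.* Chemistry is drawn at every Substudy 3 visit, and the Table 5 HBV-DNA test covers HBc Ab-positive subjects irrespective of HBs Ab. What is missing is a scheduled HBV-DNA test.
- *That M14-675 entrants are excluded from HBV monitoring.* Neither the Appendix E row nor the Figure 4 note has a study-of-origin limit. Footnote g uses the same Substudy 1 or 2 phrase for endoscopy, which M14-675 entrants plainly have. This is a drafting gap, and it matters only if M14-675 has Japan sites, which is an assumption.
- *That 8-weekly and 12-weekly testing contradict each other.* Testing every 8 weeks can satisfy a general 12-week rule, and the same sentence closes Appendix C footnote r, which is not confined to Japan. The fault is unclear application.
- *That footnote p and Table 5 are flatly opposed.* Their triggers differ, and immediate interruption is compatible with later removal from the study. They overlap only in part.

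**Conclusion.** The exemption wording is inconsistent and should be corrected. The inconsistency is confined to Japan subjects and to one of eight patterns: vaccinated, HBs Ab positive, HBc Ab positive. Read literally, Appendices C and E give that subject no scheduled HBV-DNA test, against 4 to 5 in Substudy 3 under the Figure 4 note, or 7 on footnote p's own list.

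Two things are unknown. The two rules meet in practice only if a local requirement brings the Figure 4 note into force in Japan, which the Protocol does not state. The number of subjects with this pattern is not given and may be small. The M14-675, interval and precedence points are secondary matters of clarity. Nothing here affects an endpoint, estimand, power or type I error. The case for acting is that the inconsistency bears on subject safety and is cheap to remove.

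**What to change.** Reconcile the Figure 4 double-asterisk note, Appendix C footnote s and Appendix E footnote p so that the exemption states the HBc Ab status explicitly and in identical words. At the same time:

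- say whether footnote p applies to entrants from Study M14-675;
- say to whom the 12-week sentence applies;
- cross-reference footnote p and Table 5, so that a site holding a positive PCR knows how the two instructions relate.

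Which exemption, interval and action stand is for the sponsor's medical team; no view is offered here.

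The cost is wording in four places and a letter to sites. If the reconciled text adds tests on footnote p's visit list, they are a few extra samples at visits that already draw blood. A strict 12-week schedule would fall partly on Weeks 24 and 48, which are not scheduled visits, although the Figure 4 note already allows HBV-DNA testing at unscheduled visits.
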